### 6.2.5 UPDRS Part 3 as Measured Immediately Prior to the In-clinic L-DOPA Dose

Mean change and % change Baseline (Visit 2) to each post baseline visit in the UPDRS Part 3 as measured immediately prior to the in-clinic L-DOPA dose will be evaluated as a secondary endpoint. The UPDRS Part 3 sum score will be calculated as the sum of UPDRS items 18-31 (range 0-108 points). The Part 3 sum score will only be calculated if all 27 items have been completed. In case of at least 1 missing item, the whole score will be set as missing.

The above will be summarized for the EE1 and EE2 population.

### 6.2.6 Patient Global Impression of Change (PGI-C) and Clinician Global Impression of Change (CGI-C)

The proportion of subjects improving based on the Patient Global Impression of Change (PGI-C) and Clinician Global Impression of Change (CGI-C) will be evaluated as secondary endpoints. The PGI-C and CGI-C will be analyzed by categorizing the non-missing assessments as improvements (very much improved, much improved, minimally improved) or non-improvements (no change, minimally worse, much worse, very much worse). The visits with missing assessments will be set as missing.

A Fisher's exact test will be used to compare differences between each of the active treatment group vs placebo.

PGI-C and CGI-C will be summarized for the EE1 population for each post baseline assessment.

### 6.2.7 Parkinson's Disease Questionnaire -39 (PDQ-39)

Since PDQ-39 was removed per the amendment any available data will be included in listings and no analyses will be performed.

## 6.3 Exploratory Efficacy Endpoints

The following exploratory efficacy endpoints will be presented in listings and may be analyzed post-hoc.

- Parkinson's Disease Sleep Scale (PDSS-2) overall score

The PDSS-2 overall score will be calculated as the sum of responses to the 15 questions, each scored from 0 to 4 (Never = 0, Occasionally = 1, Sometimes = 2, Often = 3, Very often =4). In case of at least 1 missing item, the overall PDSS-2 score will be set as missing.

- Total Non-motor Symptom Scale (NMSS) score

The NMSS includes 30 items on 9 different domains. For each item, the severity is rated on a scale from 0 to 3 and frequency from 1 to 4. These two ratings are multiplied to derive a final item score, ranging from 0 to 12. A domain score is calculated for each of the 9 domains as the sum of the item scores within that domain. The NMSS total score is the sum of all 30 item scores (ranging from 0 to 360).

## 6.4 Safety and tolerability endpoints

Following safety and tolerability endpoints will be evaluated. For more details, see section 15 (Analysis of safety and tolerability data).

- Safety
  - Adverse events (AEs) occurring throughout the study.

## Statistical Analysis Plan

- QTc parameters: absolute QTcF of >450 msec, >480 msec and ≤500 msec, and >500 msec, mean QTcF, changes in QTcF>30 msec and ≤60 msec, and changes in QTcF>60 msec throughout the study.
- Clinical safety laboratory (Only Creatinine Clearance, Serum Creatinine, Potassium and Magnesium), vital signs (including assessment of orthostatic hypotension), physical and neurological examination, concomitant medications throughout the study.
- Columbia-Suicide Severity Rating Scale (C-SSRS)- At baseline and Since last visit throughout the study.
- Change from Baseline (Visit 2) in impulse control disorder as evaluated by the Questionnaire for Impulsive Compulsive Disorders in Parkinson's Disease Rating Scale (QUIP-RS) throughout the study.
- Tolerability
  - The number (%) of subjects who complete the study drug
  - The number (%) of subjects who fail to complete the study drug due to AEs
  - The number (%) of subjects who fail to complete the study drug due to QTcF and QT stopping rules, seizure or convulsions.

### 6.5 PK Endpoints

Plasma concentrations of pridopidine and its metabolite TV-45065.

## 7 Sample Size Considerations

The sample size calculations for the study were based on 38 randomized subjects in each treatment group (114 randomized subjects overall) providing 80% power to detect a between-group difference of 8.5 points in the UDysRS score with standard deviation of 13 points using two sided significance level of 0.05. Assuming a drop-out rate of 15%, a total of 135 subjects were to be randomized. The sample size was calculated based on two sample t-test assuming equal variances in the two groups, using nQuery Advisor version 7.0.

Due to COVID-19 the study was terminated early.

## 8 Statistical Hypotheses

Each primary and secondary endpoint includes the comparison of each of the two dosages of pridopidine vs placebo as well as the two Pridopidine doses combined vs. placebo.

## 9 General Statistical Considerations

All data from all subjects entered into the database will be included in subject data listings. The listings will be generally sorted by study drug, center and subject number (and by visit, if applicable). In addition to the data collected on the case report form, all other study data, including data collected electronically outside of the case report form and all protocol violations will be listed.

## Statistical Analysis Plan

All applicable data will be summarized by treatment group (pridopidine 150 mg BID, pridopidine 100 mg BID, pridopidine 150 mg BID and 100 mg BID pooled active or placebo). Where appropriate, data will be summarized by visit in addition to the treatment group.

Unless otherwise indicated unscheduled or repeat assessments will not be included in summary tables, but will be included in listings. For safety analyses which summarize the total number of abnormal values over the whole study or period, the unscheduled or repeat assessments will be used for these totals, but not for the visit-specific analyses. For assessments done at the ET visit, these assessments will be used as data for the scheduled visit closest to the ET time point, in case the corresponding data are missing from this closest visit.

Unless specific otherwise, baseline is defined as the last non-missing assessment prior to the first dose of the study drug.

Continuous variables will be summarized using the number of observations (n), mean, standard deviation (SD), first quartile (Q1), median, third quartile (Q3), minimum, and maximum. Standard error of the mean (SEM) will also be provided for summaries of efficacy data, if relevant.

Descriptive statistics for categorical data will include frequency counts and percentages. The total number of subjects in the treatment group overall (N) will be used as the denominator for percent calculations, unless stated otherwise. Missing categories will be included as appropriate.

Significance testing will be 2-sided using  $\alpha = 0.05$ , unless otherwise specified.

All statistical analyses and summaries will be produced using SAS version 9.4 or higher. Deviations from the statistical plan will be reported in the clinical study report, including the rationale for the deviation.

### 9.1 Adjustment for Covariates

For the analysis of efficacy endpoints, the baseline value of the endpoint in question will be included as a baseline covariate (for continuous endpoints) or as a stratification factor (for categorical endpoints), if available. As a general rule, the last assessment before the first dose of study drug at the Baseline visit (Visit 2) will be used as the baseline covariate.

As no stratification factors were used in the randomization, the primary analyses will not include any additional covariates.

### 9.2 Handling of Drop-Outs or Missing Data

In this study, missing or incomplete efficacy data are managed in two steps. In the first step, imputation methods are defined to derive endpoints from questionnaires or diaries with incomplete data within a visit or time point. In the second step, statistical methods are defined for analysis of incomplete longitudinal datasets in case data are still missing after the first step.

### 9.2.1 Imputation of Incomplete Data within a Visit or Timepoint

- The imputation rules for the incomplete UDysRS ratings are provided in Sections 6.1 and 6.2, in order to derive the endpoints based on UDysRS.
- The imputation rules for the incomplete “ON/OFF” home diaries (i.e., diaries for days with less or more than 24 recorded hours per day) are provided in Section 6.2.1, in order to derive the relevant endpoints based on the “ON/OFF” home diaries.
- The imputation rules for the other continuous efficacy endpoints derived from questionnaires (UPDRS sum scores, PDQ-39 summary index and dimension scores, PDSS-2 and NMSS scores) are provided in Sections 6.2 and 6.3.

### 9.2.2 Handling of Missing Longitudinal Data

The following methods will be used to manage longitudinal incomplete data after the data within each visit has been imputed as described above.

- For the primary efficacy analysis, likelihood-based modeling approach will be used to handle incomplete data. For this purpose, Mixed Model for Repeated Measures (MMRM) will be applied, see Section 14.1.
- Sensitivity analyses for the primary endpoint data will be conducted using the Multiple Imputation (MI) approach. For the MI approach, each missing value will be replaced with a set of plausible values that represent the uncertainty about the right value to impute, see Section 14.1. Imputation will only be done under the assumption of Missing At Random (MAR).

Safety data will not be subject to any imputation and will be summarized on an observed case basis.

### 9.3 Interim Analyses and Data Monitoring

No interim analyses were planned.

Since the study was terminated prematurely before 30 subjects were enrolled no formal Drug Safety Monitoring Board (DSMB) meeting was conducted.

### 9.4 Multiple Comparison/Multiplicity

Since the study was terminated early and the sample size is small no adjustment for multiplicity will be performed. Statistical testing and p-values will be evaluated based on totality of information in assessing efficacy and provided primarily for descriptive purposes.

## 10 Subjects Disposition, Demographic and Other Baseline Characteristics

The following will be summarized in the Subject Disposition table.

- A summary of the number of subjects in each of the analysis populations.
- The number and percentage of subjects who were randomized but not treated.
- The count and percentage of subjects who completed or discontinued from the study or treatment. For those who discontinued from the study or treatment, the primary reason for discontinuation from the study or treatment will be presented.

Demographics and baseline characteristics will be summarized descriptively for the Safety Population, by treatment group and overall. For categorical endpoints, categories for missing data will be presented.

The following variables will be summarized:

- Demographics: age (continuous, calculated as date of informed consent minus date of birth, divided by 365.25), age categorized as <65 years versus  $\geq 65$  years, gender, ethnicity, race, height, weight, BMI (calculated as weight [kg] divided by squared height [ $m^2$ ]) and country. In case of missing day of birth, the day will be imputed as 15. In case of missing month of birth, the month will be imputed as 6.
- PD history: time since diagnosis of PD, time since start of levodopa treatment and time since onset of levodopa-induced dyskinesia, all measured in years at time of informed consent
- Report of direct observation of ON-time with dyskinesia during half-hour periods of the screening visit
- Baseline dyskinesia status: total score on UDysRS part 4 disability scale.
- Cognitive status: Mini-Mental State Examination (MMSE) total score (as categorical, % of subjects with a score of 30, 29, 28, 27, 26 or <26)
- Distribution of Modified Hoehn and Yahr stages
- Total daily levodopa dose (mg) and distribution of dosing frequency at Screening.

## 11 Prior and Concomitant Medications

Prior and Concomitant medications data are coded using WHODD Global-B3-Sep 2018 and will be presented in listings with no summary tables.

## 12 Medical History

Medical History data will be presented in listings with no summary tables.

## 13 Protocol Deviations

Protocol Deviations data will be presented in listings with no summary tables.

## 14 Analysis of Efficacy

Each primary and secondary endpoint of this study includes the comparison of each of the two dosages of pridopidine vs placebo and the two pooled active doses vs placebo.

### 14.1 Primary Endpoint

The primary endpoint of this study is the mean change from Baseline (Visit 2) to Visit 3 and Visit 5 in the sum of Parts 1, 3, and 4 of the UDysRS. The difference in the primary endpoint between the groups (pridopidine 150 mg BID versus placebo, pridopidine 100 mg BID versus placebo) will be estimated using a MMRM using the EE1 and EE2 populations after imputing missing data under assumption of MAR. The model will include the observed changes from Baseline using Visits 3, 4, 5, 6 and 7 as the response values. The treatment difference at each visit will be estimated using contrasts. The MMRM will include the treatment group (pridopidine 150 mg BID, pridopidine 100 mg BID or placebo), visit (3, 4, 5, 6 or 7) and the interaction between the treatment group and visit as fixed factors. The baseline value will be used as a covariate in the model.

A separate analysis will compare pooled active vs placebo under same assumptions as above.

An unstructured covariance structure will be applied for MMRM. In case the model will not converge with the unstructured covariance structure, heterogeneous Toeplitz structure (TOEPH), Autoregressive with heterogeneity (ARH (1)), Heterogeneous variances with Compound Symmetry (CSH), Toeplitz (TOEP), Autoregressive(1) (AR(1)) or Compound Symmetry without heterogeneous variances (CS) covariance structure will be used instead in this order. The denominator degrees of freedom will be computed using the Kenward-Roger method.

The least square (LS) means, standard errors and LS mean differences between pridopidine 150 mg BID versus placebo and pridopidine 100 mg BID versus placebo at each visit along with the 95% confidence intervals (CIs) will be provided. The nominal p-values for the hypothesis testing will also be provided. Treatment difference will be assessed with a 2-sided alpha level of 0.05.

The EE1 and EE2 populations will be used for the primary efficacy analysis.

The above analysis will be conducted after imputation of missing data using multiple imputations (MI) under MAR assumption: This methodology will structure data based on missing data patterns. The method will be based on a missingness pattern having a monotone structure, i.e. if among the observations over time one data value is missing, all other values after this missing value will also be treated as missing. For subjects with intermittent missing values, before performing MI, a monotone missingness pattern will be generated. Intermittent missing values will be imputed using the Markov Chain Monte Carlo (MCMC) methodology which assumes a multivariate normal distribution over all variables included in the imputation model. The MI procedure in SAS will be used for this purpose and this first MI step is planned

to be repeated 100 times, creating several different datasets with a monotone missing data structure. Seed value of 1995 will be used in the MI procedure. The imputation is based on the MAR assumption, i.e. the missing data are assumed to follow the same model as the other subjects in their respective treatment arm.

After this, the remaining missing data will be imputed using a method for monotone missingness, also based on the MAR assumption. Thus, for each of the created dataset with a monotone missing data pattern, the MI procedure in SAS will be used to impute missing values based on a sequential procedure reflecting the monotone missing data pattern. Subjects with the first missing value occurring at Visit 3 will have their missing Visit 3 value replaced by an imputed value from a regression model with treatment group and the baseline value as explanatory variables. In the next step, subjects with their Visit 4 value missing will have their missing Visit 4 value replaced by an imputed value from a regression model with treatment group, baseline value and the Visit 3 value as explanatory variables. In the next step, subjects with their Visit 5 value missing will have their missing Visit 5 value replaced by an imputed value from a regression model with treatment group, baseline value and the Visit 3 and Visit 4 values as explanatory variables. Similar procedure will be used to replace the missing values at Visit 6 and 7.

The imputed datasets generated with the approach described above do contain only non-missing values and are used as input in the model for the sensitivity analysis of the primary endpoint. MMRM models similar as described for the primary analysis will thus be run on each of the 100 generated imputed datasets and the difference between the treatment groups at Visit 7 will be estimated. Finally, the MIANALYZE procedure in SAS will be applied to combine the results from these analyses to derive overall estimates of the treatment differences at Visit 7. In addition to the estimates, corresponding 95% confidence intervals and p-values will be calculated.

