## 6.1 Primary Endpoint: Sum of Parts 1, 3, and 4 of UDysRS

The primary endpoint is the mean change and % change from Baseline (Visit 2) to Week 3/5 (Visit 3) and Week 8/10 (Visit 5) in the sum of Parts 1, 3, and 4 of the Unified Dyskinesia Rating Scale (UDysRS) while the patient is in the peak “ON” state and experiencing maximal peak dose dyskinesia.

The sum of Parts 1, 3, and 4 of the UDysRS will be calculated as the sum of Part 1 (historical disability of ON-dyskinesia impact), Part 3 (objective impairment) and Part 4 (objective disability). The sum scores will be calculated as follows:

- Part 1: sum of UDysRS items 1-11; 0-44 points
- Part 3: sum of UDysRS items 16-22; 0-28 points
- Part 4: sum of UDysRS items 23-26; 0-16 points.

For the sum scores of Parts 1, 3 and 4, the following imputation rules will be used in case of incomplete data:

- Part 1: Part 1 is sum of Part 1A (item 1) and Part 1B (items 2-11)
  - If Part 1A (item 1) is missing, the Part 1 sum score will be set as missing.
  - If there is one missing item in Part 1B (items 2-11), the missing item will be replaced by the average of the non-missing items 2-11 from the same subject.
  - If there is more than one missing item in Part 1B (items 2-11), the Part 1 sum score will be set as missing.
- Part 3:
  - If there is one missing item in Part 3 (items 16-22), the missing item will be replaced by the average of the non-missing items 16-22 from the same subject.
  - If there is more than one missing item in Part 3 (items 16-22), the Part 3 sum score will be set as missing.
- Part 4:
  - If there is one missing item in Part 4 (items 23-26), the missing item will be replaced by the average of the non-missing items 23-26 from the same subject.
  - If there is more than one missing item in Part 4 (items 23-26), the Part 4 sum score will be set as missing.
- Sum of Parts 1, 3 and 4:
  - The sum of Parts 1, 3 and 4 will be calculated only if sum of Part 1, sum of Part 3 and sum of Part 4 are all non-missing, after applying the imputation rules presented above. Otherwise, the sum of Parts 1, 3 and 4 will be set as missing.

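### SAP Section 14.1 pools the multiple-imputation result only at Visit 7, not at primary Visits 3 and 5, and leaves unclear whether imputation is primary or sensitivity

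*SAP*

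**What the plan says.** **Time point.** Section 14.1 opens with "The primary endpoint of this study is the mean change from Baseline (Visit 2) to Visit 3 and Visit 5", and Section 6.1 gives the same two visits. Section 3.1 puts the primary objective at Visit 5, with a further comparison at Visit 3. The last paragraph of Section 14.1 covers estimation and pooling from the imputed datasets. There "the difference between the treatment groups at Visit 7 will be estimated", and the MIANALYZE step is used to "derive overall estimates of the treatment differences at Visit 7". No other visit is named in that paragraph.

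**Role of imputation.** Section 9.2.2 handles incomplete data in the primary analysis by the likelihood-based MMRM and assigns multiple imputation to the sensitivity analyses. Section 14.1 says four things:

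- The primary MMRM is fitted "using the EE1 and EE2 populations after imputing missing data under assumption of MAR".
- In the same paragraph, "The model will include the observed changes from Baseline using Visits 3, 4, 5, 6 and 7 as the response values".
- The imputation text begins "The above analysis will be conducted after imputation of missing data using multiple imputations (MI) under MAR assumption".
- The completed datasets are "used as input in the model for the sensitivity analysis of the primary endpoint".

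**The concern.** The sensitivity analysis of a primary endpoint should address that endpoint. As written, the only pooled imputation estimate is at a visit that is no longer primary. Visit 7 is also a poor choice in a trial stopped early: under monotone loss it has the fewest observed values and depends most on imputation.

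The second problem is that the primary analysis is not uniquely defined. One analyst could follow Section 9.2.2 and report the MMRM on observed data. Another could follow the opening of Section 14.1 and report a pooled estimate from 100 imputed datasets. Both would be following the SAP and they would get different numbers. SAP Section 9.4 drops multiplicity adjustment, so fixing one primary analysis before unblinding is one of the main remaining protections against choosing between results.

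**Working it through.** **Step 1. Time points side by side.**

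| SAP text | Visits named |
|---|---|
| 6.1, primary endpoint | 3 and 5 |
| 14.1, opening sentence | 3 and 5 |
| 14.1, MMRM contrasts | each visit |
| 14.1, estimation from imputed datasets | 7 |
| 14.1, MIANALYZE pooling | 7 |
| 14.2.1, continuous secondary endpoints | 7, plus 3, 4, 5 and 6 |

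The estimation and pooling paragraph names Visit 7 twice and Visits 3 and 5 not at all. Section 14.2.1 expressly adds the earlier visits; this paragraph does not. Protocol Section 7.1 had Visit 7/ET as the primary time point, so the wording may be a carry-over. That is an inference.

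**Step 2. Role of imputation side by side.**

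| SAP text | Primary analysis uses | Imputation is |
|---|---|---|
| 9.2.2 | likelihood-based MMRM | sensitivity |
| 14.1, second sentence | MMRM on imputed data | primary |
| 14.1, third sentence | observed changes | not in the model |
| 14.1, start of imputation text | imputed data for the analysis just described | primary |
| 14.1, last paragraph | (not stated) | sensitivity |

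If imputation were primary, the sensitivity analysis would fit a similar MMRM to the same imputed data and would add nothing. Protocol Section 7.9.1 specified no imputation, but SAP Sections 2 and 17 say that the SAP supersedes the protocol, so the protocol cannot settle the conflict.

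**Step 3. Where values can be missing.** EE1 requires treatment at Visit 3 and some post-randomization primary assessment (Section 5.1), so Visit 5 can be missing. EE2 requires treatment at Visit 5 and a valid assessment. The main exposure is therefore Visit 5 in EE1. The documents give no counts of missing values.

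**Step 4. Planning figures.** The SD of 13 and difference of 8.5 come from SAP Section 7. The stated sample size reproduces: a two-sample t-test with two-sided alpha 0.05 and 80% power needs 37.7, so 38 per arm (power 80.3%), and 114 / 0.85 = 134.1, so 135. This confirms the inputs but has no bearing on the point itself.

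**Step 5. How far apart the two readings fall.** A simulation compared them on the same data at Visit 5.

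- From the SAP: SD 13, five post-baseline visits, sequential regression imputation, 100 imputations.
- Assumed: 9 per arm (27 in total; Section 9.3 says fewer than 30 enrolled), between-visit correlation 0.6, no true effect, and 10% to 40% of Visit 5 values missing. Loss is monotone and administrative, half of it (rounded down) before Visit 4 and the rest before Visit 5.
- Reading A: MMRM on observed data with arm-by-visit means, a baseline slope and unstructured covariance, fitted by maximum likelihood.
- Reading B: the same MMRM on each imputed dataset, with the estimates averaged.
- Measure: |A − B| over both dose contrasts, 40 trials per scenario.

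| Missing at Visit 5 | Median gap (points) | 90th percentile (points) |
|---|---|---|
| 10% | 0.19 | 0.60 |
| 20% | 0.29 | 0.84 |
| 30% | 0.47 | 1.61 |
| 40% | 0.86 | 2.75 |

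Repeats with separate code gave medians of 0.2, 0.4, 0.5 and 0.8 (30 trials per scenario) and 0.20, 0.29, 0.42 and 0.85 (60 trials). Their 90th percentiles were 0.8, 1.4, 1.2 and 2.5, and 0.58, 1.03, 1.41 and 2.99. The medians are stable; the upper tails are imprecise with so few trials.

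**Step 6. Yardsticks.** At 40% missing, the median gap is 0.86 / 8.5 = 10% of the design difference and the 90th percentile is 2.75 / 8.5 = 32%. The sampling SD of the Visit 5 difference in the 60-trial run was 5.4 to 6.4 points; the unadjusted complete-data value is 13 × √(2/9) = 6.1. The median gap is then about 4%, 5%, 7% and 13% of sampling noise as missingness rises. The mean signed difference stayed within 0.3 points in every scenario.

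The simulation sizes only the question of role. The Visit 7 problem is one of wording and has no numerical size that the documents would allow us to compute.

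**The case against.** The strongest reply is that little of substance is lost. Section 14.1 promises LS mean differences, confidence intervals and p-values at every visit. If imputation is part of the primary analysis, that promise arguably carries over to the imputed results and the Visit 7 wording is only narrower. If imputation is the sensitivity analysis, only a sensitivity check is affected. Both readings assume MAR with nearly the same model, so they target the same quantity and differ by a small fraction of the sampling error. The EE definitions leave few missing values at Visit 3 in EE1 or Visit 5 in EE2. The study is now a proof of concept, and its p-values are mainly descriptive.

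Much of this stands, and it limits the consequence. It does not make the text consistent. The one paragraph on pooling, followed as written, yields no imputation estimate at either primary visit. MMRM and imputation under MAR agree only approximately with fewer than 30 patients. Descriptive p-values do not remove the need to know which estimate is the primary one; Section 14.1 still assesses differences at a two-sided 0.05 level.

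It is also fair to say that either role for imputation could be defended. The preference for observed data rests on Section 9.2.2, the final paragraph of Section 14.1 and the observed-changes sentence, not on the superseded protocol.

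**Conclusion.** The concern holds on both parts. The imputation result is specified at the wrong visit for the primary endpoint, and the SAP gives conflicting accounts of whether imputation belongs to the primary or the sensitivity analysis. The primary MMRM results at Visits 3 and 5 survive, so this should be fixed but does not invalidate the analysis.

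The likely numerical effect is small with little missing data and grows with loss before Visit 5. The median gap between readings is about 0.2 to 0.9 points, and the 90th percentile about 0.6 to 2.7, with no evident bias. Those figures rest on the assumed 9 per arm, correlation of 0.6 and 10% to 40% missingness. The finding about the text rests on no assumption.

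**What to change.** Amend the SAP before unblinding, which Section 2 says is still ahead:

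1. In Section 14.1, state that the primary analysis is the MMRM on observed changes without imputation, in line with Section 9.2.2, and delete the clause that fits it after imputation.
2. Reword the opening of the imputation text so that multiple imputation is the sensitivity analysis throughout.
3. In the final paragraph, name Visit 3 and Visit 5 in both the estimation and the MIANALYZE sentences, for each dose versus placebo and for pooled active versus placebo. Visit 7 may stay as an addition.

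The imputation steps through Visit 7 need no change, because the MMRM uses Visits 3 to 7. The cost is a few sentences and the corresponding contrasts from analyses already planned. No new data are needed.
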